10.2. Data collection overview

The documentation of study data will be reported by the attending physician via paper or electronic case report form (CRF).

Term	Baseline visit (V1)	Observational visit (V2)	Observational visit (V3)	Final Observational visit (V4)
Inclusion/exclusion criteria	X			
Signed Informed consent form	X			
Date of visit	X	X	X	X
Demographic information	X			
Medical history (incl. risk factors, prior diseases, prior HTN therapy etc)	X			
Body Mass Index (BMI)	X	X	X	X
Physical examination and vital signs*	X	X	X	X
HTN therapy (drugs, doses)	X	X	X	X

Laboratory tests and instrumental exams*	X	X	X	X
Concurrent medical conditions	X			
Concomitant medication		X	X	X
Adverse events		X	X	X

* All examinations (physical examination and vital signs, laboratory tests and instrumental exams) are done in accordance with clinical routine practice and physician's decision. Instrumental exams are measurement of blood pressure, heart rate, ECG, 24-hour ambulatory blood pressure monitoring. All examinations should be registered in the CRF only if they are done in routine practice.

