- Physical examination and vital signs: height (cm), weight (kg), waist circumference (cm), body mass index, systolic and diastolic blood pressure (position, time, values), heart rate
- HTN treatment:
 - monotherapy/combination treatment,
 - Edarbi® dosage regimen,
 - other HTN co-medications: INN, trade name, dosage regimen.
- Laboratory data (last available measurements, if done within routine practice):
 - total cholesterol
 - triglycerides,

- low-density lipoproteins,
- high-density lipoproteins,
- blood glucose,
- serum creatinine,
- urea,
- glycated haemoglobin.
- Concomitant diseases
- Concomitant medication: INN, trade name, dosage regimen (single and total daily dose), duration of treatment, indication for administration
- Adverse events: seriousness, severity, causality, start and stop dates, action, outcomes

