10.6.6. Pregnancy

If any patient is found to be pregnant during the study she should be withdrawn. The pregnancy should be reported immediately, using an AE report form.

All pregnancies in patient on active study drug will be followed up to final outcome. The outcome, including any premature termination, must be reported to the Sponsor. An evaluation of child wellness after the birth must be reported to the Sponsor.

10.7. Laboratory, instrumental exams, physical examination and vital signs to be documented in the study

All examinations (physical examination and vital signs, laboratory tests and other exams) will be performed in accordance with common clinical routine practice, routine practice of a particular medical institution. All examinations are solely based on the physician's decision about strategy of diagnostics and treatment.

All examinations should be registered in the CRF only the protocol required lab tests will be recorded in the CRFs if they are done in routine practice. The documentation of laboratory and instrumental tests will strictly follow clinical practice. The reference ranges for each protocol required lab test performed according to routine practice will be collected as well.

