13.2.5. Data handling

13.2.5.1. Missing data and invalid data

Missing data will not be restored. No procedures for missing data pattern assessment and/or imputation are planned. Outlier detection will be performed during blind data review, using modified Z-score([32] calculation

$$M_i = \frac{0.6745(x_i - \tilde{x})}{\text{MAD}},$$

with MAD denoting the median absolute deviation and \tilde{x} denoting the median.

Values of modified Z-score >3.5 will be considered outliers for univariate data sets that are assumed to follow an approximately normal distribution. If the normality assumption for the data being tested is not valid, then a determination of outlier using interquartile range and median (values more than 1.5 times the interquartile range will be considered outliers). Outliers will not be excluded from primary analysis *en bloc*, however, the medical context for each outlier will be defined and appropriate action taken. List of outliers flagged and actions taken will be included into Statistical Analysis Report. An additional sensitivity analysis will be performed excluding outliers.

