5. STATISTICAL / ANALYTICAL ISSUES

Visit windows

In accordance with the protocol, due to the non-interventional study design it's not possible to appoint exact times for the study visits, although it is expected that the period of observation will be approximately 6 months. The frequency of the visits will be assigned by each physician according to their routine practice. It is anticipated that the patients will visit their physician every 3 months and more often at the beginning until the patient achieves target blood pressure.

So, for the analysis and summary of clinical laboratory, efficacy, and safety data in case of this analysis/summary performed on "by visit" base. In the event of multiple values for an assessment within an analysis window, the value closest to the scheduled visit date will be used for analyses. If two values tie as closest to the time point (for example, one value is before and the other value is after the time point), then the later value will be selected as the analysis value.

Analysis Window	Start	End	Target Asses dupli	sment to be used if cates	
Baseline visi	t <1		NA		
Month 1 Month 3 Month 6	2 46 136	45 135 NA	30 90 Closes 180 equidi	st to target day, if stant use later result.	

The definition for the study days included in each study window is defined as below:

Treatment Day prior to first dose = Visit Date – Date of First Dose

Treatment Day on or after first dose = Visit Date – Date of First Dose + 1

Adjustments for Covariates

No specific adjustments for covariates will be made in all statistical analyses, unless specified otherwise per-analysis level.

Handling of Dropouts or Missing Data

Missing efficacy outcomes will be assumed to be missing at random (MAR) and thus will not be imputed in the primary analysis. However, if greater than 1% of all primary/secondary outcomes that should be available for analysis are missing, a sensitivity analysis will be undertaken in addition to the primary MAR analysis.

Confidential

This sensitivity analysis will include an evaluation of the results of models developed under the assumptions of:

1) last observation carried forward;

2) worst extreme case imputation and;

3) regression model imputation using all available information.

Outlier identification

During data Quality Control outlier identification will be performed using adjusted Z-score method (Iglewicz and Hoaglin, 1993).

$$M_i = \frac{0.6745(x_i - \tilde{x})}{MAD}$$

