- Changes in serum creatinine, eGFR (CKD-EPI), urea, total cholesterol, triglycerides, low density lipoproteins, high density lipoproteins (from baseline to Month 1- Month 3- Month 6) will be assessed and presented in summary tables using descriptive statistics for continuous variables. Additionally the changes of this variable will be analyzed with paired T-test in pairwise comparisons with baseline level of the variable.
- Changes of blood glucose level, glycated hemoglobin (HbA1c) from baseline to the visits 2, 3, and 4. For the analysis 95% Cis will be constructed. Additionally the changes of this variable will be analyzed with paired T-test in pairwise comparisons with baseline level of the variable.

9.0 Analysis of BMI and waist circumference change from baseline to visit 4. 95% CIs will be constructed. Additionally the changes of this variable will be analyzed with paired T-test in pairwise comparisons with baseline level of the variable.

10. Reasons for discontinuation of Edarbi[®] therapy will be described and presented in summary tables using absolute frequencies and percentages as well as 95% confidence intervals.

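### Paired t-tests on laboratory changes use only patients the physician chose to re-test; if re-testing favours abnormal baseline values, the result is biased towards improvement

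*SAP*

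**What the plan says.** SAP 9.2 lists "Changes in serum creatinine, eGFR (CKD-EPI), urea, total cholesterol, triglycerides, low density lipoproteins, high density lipoproteins" as changes to be assessed from baseline to Months 1, 3 and 6, and adds: "Additionally the changes of this variable will be analyzed with paired T-test in pairwise comparisons with baseline level of the variable". The next item applies the same test to blood glucose and HbA1c. SAP section 11 asks for the p-value of each change from baseline, and SAP 9.3.1 repeats the items of 9.2 across a long list of subgroups.

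Whether a value exists is not set by the plan. Protocol 10.7 says: "All examinations are solely based on the physician's decision about strategy of diagnostics and treatment". The footnote in Protocol 10.2, repeated in SAP 2.1, says: "All examinations should be registered in the CRF only if they are done in routine practice". Protocol 10.3 and 10.4 describe what is entered, at baseline and again at Visits 2 to 4, as "Laboratory data (last available measurements, if done within routine practice", with no requirement that a later entry come from a new sample.

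On missing data, SAP section 5 says: "Missing efficacy outcomes will be assumed to be missing at random (MAR) and thus will not be imputed in the primary analysis". It adds that "if greater than 1% of all primary/secondary outcomes that should be available for analysis are missing, a sensitivity analysis will be undertaken", using last observation carried forward, worst-case imputation and regression imputation. Protocol 13.2.5.1 says: "No procedures for missing data pattern assessment and/or imputation are planned". SAP section 5 makes no covariate adjustment unless an analysis specifies it, and none is specified for laboratory variables. The mixed model in SAP 9.1 covers clinic SBP and DBP only. There is no control group (Protocol 9.3).

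**The concern.** A paired t-test answers a question about patients who have both values. Here a clinician decides who they are, possibly after seeing the first value. If patients with a high V1 LDL, glucose or creatinine are the likelier ones to be tested again, the re-tested group starts above the cohort mean and drifts back on the second measurement. For HDL and eGFR abnormal means low, so the group starts below the mean and drifts up. Either way the drift looks like improvement.

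With no control arm, nothing in the comparison absorbs the drift. The missing-at-random assumption does not help either: when missingness depends on V1, the mean of complete pairs is biased even though the data are missing at random. The bias discussion in Protocol 13.2.4 deals with early leavers and their last blood pressure, not with selective re-testing.

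At stake is a small p-value for a lipid, glucose or renal change that comes from the testing pattern. Protocol 5.2.2 suggests beneficial metabolic effects of the drug, so such a result could be read as support for them.

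**Working it through.** **Sizes used.** The documents give no sample size for laboratory variables. The only stated target is for SBP (Protocol 13.4). It reproduces: the SD of the paired difference is 17.79 × √(2 × (1 − 0.4375)) = 18.87 mm Hg; a 95% CI half-width of 1 mm Hg with probability 0.9 needs 1437 pairs (actual probability 0.903); and 1437/0.75 = 1916. I take 1437 as the pooled size. SAP 2.4 and section 4 restrict this SAP to Kazakhstan and give no number. Protocol 7.2 plans about 10 of about 90 sites there, so I assume 1437 × 10/90 ≈ 160.

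**Assumed inputs (not in the documents).**
- No true change, and normal values with equal variance at both visits.
- Within-patient correlation r from 0.6 to 0.9.
- Re-test probability *a* on the abnormal side of the V1 median and *b* on the other side, at 80%/30% or 60%/40%.

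**Formulas, in V1 SD units.**
- Mean V1 of re-tested patients: m = √(2/π) × (a − b)/(a + b)
- Expected paired change towards improvement: (1 − r) × m
- SD of the paired change: √[(1 − r)²(1 − m²) + (1 − r²)]
- Pairs: n = N(a + b)/2. Two-sided rejection comes from the noncentral t with noncentrality (change/SD) × √n.

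**Worked case, 80%/30%, r = 0.7.** m = 0.798 × 0.5/1.1 = 0.363. Bias = 0.3 × 0.363 = 0.109. SD = √(0.09 × 0.868 + 0.51) = 0.767. For N = 160, n = 88, noncentrality 1.33, rejection 26%. For N = 1437, n = 790, noncentrality 3.99, rejection 98%.

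| Re-test rates | r | Bias (SD) | p<0.05, N = 160 | p<0.05, N = 1437 |
|---|---|---|---|---|
| 80%/30% | 0.6 | 0.145 | 33% | >99% |
| 80%/30% | 0.7 | 0.109 | 26% | 98% |
| 80%/30% | 0.8 | 0.073 | 19% | 90% |
| 80%/30% | 0.9 | 0.036 | 12% | 63% |
| 60%/40% | 0.6 | 0.064 | 10% | 48% |
| 60%/40% | 0.7 | 0.048 | 8–9% | 38% |
| 60%/40% | 0.8 | 0.032 | 7% | 27% |
| 60%/40% | 0.9 | 0.016 | 6% | 16% |

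Simulation gave the same picture (about 6–35% at 160 and 17–99% at 1437). When re-testing is unrelated to V1 (50%/50%), m = 0, the bias is zero and rejection is nominal.

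**Alternatives, simulated with no drug effect.**
- Carrying V1 forward shrinks the mean change but leaves the rejection rate unchanged (26% and 98% in the worked case).
- A model with V1 as a response, so that patients tested only at V1 contribute, gives a mean of 0.00 SD and about 5% rejection.
- That model fails if old values are entered as new visits. In the worked case at N = 1437, if 25%, 50% or 100% of patients not re-tested have V1 carried over, it gives −0.036, −0.050 and −0.060 SD and rejects in about 35%, 74% and 98%. It was never worse than the paired test, but it needs a rule on sample dates.

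**The case against.** The strongest objection is that selection on V1 is assumed. No section says repeats follow abnormal results. Protocol 10.7 also refers to the routine of the particular institution, and testing by a fixed clinic routine would produce no such bias. The correlations and re-test rates are also supplied from outside. This stands, so the point is conditional.

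Second, a reader might take the 98% figure as this SAP's error rate, or infer that the test will report an improvement. Neither is supported. The figure belongs to the pooled size and one strong re-test pattern. At the assumed Kazakhstan size the excess over 5% runs from slight to moderate, and SAP 2.4 already warns of small numbers.

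Third, a reader might infer that these tests serve the study's stated rationale. Protocol 5.3 concerns blood pressure control. The metabolic claims are in the drug background (5.2.2) and rest on preclinical work.

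Fourth, the plan has some safeguards. Regression imputation could remove the bias if V1 is in the model. However, the trigger covers primary and secondary outcomes that should be available. Laboratory changes are absent from the secondary list in SAP 2.3.1 although they sit under the 9.2 heading, and an optional test is arguably never due. Even if triggered, the analysis would sit beside the reported t-test. Mock Table 2 in SAP section 11 would give counts for values and changes by visit, and value minus change roughly recovers the paired patients' baseline mean, so part of the needed description already exists.

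Finally, the exploratory lists are redacted and the analyses under SAP 9.3.2 are not shown, so another laboratory model cannot be excluded.

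**Conclusion.** The point holds in conditional form. The planned test is biased towards improvement if re-testing is more likely after an abnormal V1 value, and the visible plan neither prevents this nor clearly shows whether it happened. Under the stated assumptions the bias is about 0.02 to 0.145 SD. False significance is about 6% to 33% at the assumed Kazakhstan size of 160, and about 16% to over 99% if the same test is used on the pooled 1437. The documents do not support saying that the bias will occur, nor that pairs are formed only from repeat tests, since an old result may be entered again at a later visit. The blood pressure outcomes are outside this point. A better method is available at little cost, so the SAP should be amended.

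**What to change.** In SAP 9.2, for creatinine, eGFR, urea, lipids, glucose and HbA1c:

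1. Replace the paired t-test with a longitudinal mixed model in which the V1, V2, V3 and V4 values are all responses, and report each visit-minus-V1 contrast with its 95% CI. Patients tested only at V1 then contribute. Copying the blood pressure model, with baseline as a covariate, is not enough: with one follow-up visit, evaluating it at the mean V1 of included patients reproduced the full bias (−0.108 SD in the worked case).
2. Count a V2 to V4 value only if its sample date is after V1, and treat carried-over results as missing.
3. Tabulate the V1 mean in re-tested and not re-tested patients, beside the counts already planned.

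The cost is SAP wording and a standard model; SAP section 11 already mentions proc mixed output. No additional test is asked of any patient, so the non-interventional design is untouched. There are two limits. The model still assumes that re-testing depends only on recorded values. It also needs sample dates, which Protocol 10.3 and 10.4 do not list among the data collected; if the CRF does not hold them, new samples cannot be identified and the results should carry that caveat.

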9.3 Additional methods of analysis

9.3.1 Subgroup analyses. Primary efficacy variable as well as the variables listed at the items 1-10 in the section 9.2 will be analyzed both in general population and in the following subgroups (if applicable):

- patient sex (male/female);
- patient age (60 or more, <60 years old);
- BMI (normal (<25); overweight (25-30), obese (>30_) and according to grade of obesity (grade I 30-34,9; Grade II 35-39,9; Grade III ≥40)
- metabolic syndrome (yes, no),
- diabetes mellitus (yes, no),
- diabetes mellitus, impaired glucose tolerance or normal glucose metabolism
- subgroups with different eGFR according to CKD-EPI (eGFR <30; 30-59 and >=60);
- subgroups according to previous antihypertensive treatment (treated/not treated and treated patients according to class of antihypertensive treatment used before initiation of Edarbi); the group of patients who was treated with RAAS blocker monotherapy and the group of patients who was treated with combination of RAAS blocker and diuretic and the group of patients who was treated with RAAS blocker and Calcium channel blocker to be described separately.
- patients with newly diagnosed hypertension
- The subgroup of patients with isolated systolic hypertension (patients not treated with antihypertensive treatment before the study who has SBP ≥140 mm Hg and DBP <90 mmHg at visit 1).
- diabetes mellitus or metabolic syndrome or nothing;
- Subgroup of Patients with Chronic heart failure and patients without chronic heart failure in diagnosis
- Subgroups according to risk factors: smokers/non-smokers; family history of cardiovascular disease (yes/no)
- Subgroups according to target organ damage by HTN (yes/no; if yes according to organs involved (heart, kidney, brain, eyes, vessels).

- Subgroups according to antihypertensive treatment initiated at baseline level: monotherapy with azilsartan and patients receiving combination therapy with azilsartan (both in general and according to type of used combination (double therapy; triple therapy, other) and per classes of used in combination))
- Subgroups of patients who was initiated with different doses of azilsartan at baseline. In addition to the variables listed above the following is to be evaluated in every baseline dose group: % of patients receiving different doses of Edarbi at visits 1, 2,3,4; % of patients receiving monotherapy; double, triple and more therapy at visits 1,2,3,4; distribution of classes used in combination therapy at visits 1,2,3,4: distribution of dosages used per region of site location
- Subgroup of patients who were maintaining initially prescribed dose of Edarbi throughout all the study duration namely: the group irrespective of the dose of Edarbi and type of therapy (combined or monotherapy); the groups according to Edarbi dose irrespective of the type of therapy (combined or monotherapy); the groups according to both Edarbi dose and the type of therapy (combined (double; triple or more or monotherapy);
- The group of patients who was prescribed the dose 20 mg at baseline; In addition to variables listed above the following information is required regarding this group: change of the dose at every visit; % of patients who were maintaining at the dose 20 mg until the end of the study; antihypertensive treatment before baseline: monotherapy or combination therapy (with description of the combinations according to the drugs used and types of combinations (double, triple etc); Additionally the following subgroups are to be analyzed: patients prescribed 20 mg who received no antihypertensive medication before; patients prescribed 20 mg who received any antihypertensive medication before baseline.
- The group of patients who achieved BP target of <140/90 mmHg at any of the timepoints of the month 1, 3, 6 vs patients who didn't achieve it
- The group of patients who achieved the target SBP of <130/80 at the month 1, 3, 6 vs patients who didn't achieve it.
- The group of patients who achieved SBP<140 or change>=20 at any of following timepoints: Month 1, Month 3, month 6).

- The group of patients who achieved DBP<90 or change>=10 (at any of the following timepoints: Month 1, Month 3, month 6
- The group of patients who achieved SBP<140 or change>=20 and DBP<90 or change>=10 at any of the following timepoints: Month 1, Month 3, month 6
- The group of patients with fasting hyperglycemia during the study
- The group of patients who reduced the weight during the study vs those who didn't reduce the weight
- The subgroups of patients: patients who wasn't receiving statins throughout the course of the study; patients who received statins throughout the study course without changes of drugs of doses; patients who received statins throughout the study and has had escalation of the dose or change in drug
- The subgroups according to level of urbanization: >1 000 000 citizens; 250 000-1 000 000; 100 000-250 000; 50 000-100 000; <50 000
- **9.3.2.** Additional exploratory analyses. The following exploratory analyses are additionally planned:

10. SAFETY ANALYSES

Unless specifically stated otherwise, the Safety Set (patients who have taken at least one dose of Edarbi®) will be used for all safety summaries and analyses.

All safety data will be included in data listings.

For relevant safety variables, early Withdrawal Visits will be assigned to the closest scheduled visit for the particular assessment that is being summarized.

Adverse Events

Prior to analysis, adverse drug reactions will be coded using MedDRA.

Incidence and characteristic of adverse drug reactions will be described and presented in summary tables using absolute frequencies and percentages;

Evaluation of AEs will consist of the determination of total number of AEs, total number of patients with at least one AE and the number of AEs, the number of patients with AE leading to discontinuation of the study treatment. The incidence and severity of all AEs will be summarized by System Organ Class and Preferred Term within SOC. Treatment discontinuation due to AEs will be tabulated

AEs reported in the study as well as AEs reported directly to authorities and to Takeda International Drug Safety according to section 11.3 and not captured in the study database will be extracted from the overall safety database and the study database and listed or tabulated in the final report in the standard way of presenting such data in a Periodic Safety Update Report (PSUR). In addition AEs will be tabulated for Edarbi treatment doses (if any dosage groups, e.g. 40 mg and >40-80 mg will be determined).

Interim safety analysis will be based on the data of first 470 patients who either achieved final study visit or discontinued the study.

